#### 6.1.2 Formulation, Packaging, and Labelling

GTx-024 3.0 mg Softgels will be supplied as opaque, white to off-white, size 5, oval Softgels with "GTx" imprinted in black ink on the outer shell containing 3.0 mg of GTx-024. The liquid Softgel fill is composed of GTx-024 dissolved in polyethylene glycol 400. GTx-024 3.0 mg Softgels will be packaged in blister packs. Each blister pack will contain sufficient study drug for one (1) week of dosing. At baseline, Visit 4 (week 8), Visit 6 (week 16), Visit 8 (if subject continues treatment after week 24), and thereafter (if subject continues treatment every 8 weeks), subjects will be provided with a carton of study drug containing 10 blister packs, equivalent to 10 weeks of dosing. Subjects will be requested to bring with them the carton box with all blister packs at every visit.

Each blister pack will be comprised of 2 blister strips (for 18 mg treatment) encased in a child-resistant heat-sealed card. The blister strips are composed of a PVC/ACLAR base and an aluminum foil/PVC/PVAC copolymer and polymethacrylate (product contact) lidding. Perforations on the back of the heat-seal card overlay the foil lidding. To remove the study drug, subjects will release the appropriate perforation by depressing a release button on the inside of the card. Once released, the perforation can be removed and the study drug pushed through the foil.

Dosing instructions will be provided on the study drug label and in the subject information sheet.

#### 6.1.3 Product Storage and Stability

Recommended storage will be at controlled room temperature 15°C–25°C (59°F–77°F), with excursions permitted to 30°C (86°F), protected from moisture.

### 6.2 Dosage, Preparation, and Administration of Study Intervention/Investigational Product

Six (6) GTx-024 3.0 mg Softgels for an 18 mg daily dose will be taken PO with water at approximately the same time each day, with or without food.

Protocol: A Phase 2 Open Label, Multi-Center, Multinational Study Investigating The Efficacy and Safety Of GTx-024 On Advanced, Androgen Receptor-Positive Triple Negative Breast Cancer (AR+ TNBC)	Compound No.: GTx-024 Author: [name]
---	---

In the event of a dose reduction, to 9 mg, three (3) GTx-024 3.0 mg Softgels will be taken daily, PO with water at approximately the same time each day, with or without food.

### 6.3 Modification of Study Investigational Product Dosing for a Subject

With the exception of elevated LFTs and hypercalcemia, both of which are further addressed below, subjects who experience an AE with Grade  $\geq 3$  intensity (NCI-CTCAE, Version 4.0) and/or intolerance may have a dose reduction from 18 mg to 9 mg per day or a drug interruption based on the medical judgment of the Investigator and after confirmation by the study Medical Monitor. The drug interruption may last for a period of up to 7 days after which the subject must be rechallenged with study drug (18 mg or 9 mg) or discontinued from the study. In the case of a dose reduction, once the AE has resolved or reduced in intensity to Grade 1, the subject may be rechallenged with 18 mg or maintained at 9 mg at the discretion of the Investigator.

For  $\geq$  Grade 3 elevations in LFTs, study drug should be held. A recheck of LFTs should be done within 48 hours. At the discretion of the investigator, study drug may be restarted at the 18mg dose or reduced to a 9mg dose when the LFTs have resolved to Grade 1 or better.

In the event of hepatotoxicity, please also refer to [Section 9.4](#) [Halting Rules](#).

In the event of  $\geq$  Grade 2 hypercalcemia, study drug should be held until hypercalcemia resolves to Grade 1 or better.

### 6.4 Accountability Procedures for the Study Investigational Product(s)

The Investigator is responsible for the correct storage of study medication according to GTx, Inc. recommendations. The study medication made available for this clinical trial must be used in accordance with the protocol and dispensed only under the supervision of the Investigator and documented sub-Investigators. The Investigator must maintain complete and accurate records, showing the receipt and disposition of all supplies of the study medication delivered by the GTx, Inc. authorized representative. These records must include a master record which lists the date of receipt of all study medication shipments, batch numbers, expiration date, and quantities received. In addition, a dispensing record which includes all quantities dispensed, identification of the person to whom study medication was dispensed, the date of each dispensing, and the identification of the dispenser will also be maintained. The master dispensing records are separate from records kept for individual trial subjects.

It is the Investigator's responsibility to ensure that study medication used by trial subjects plus unused study medication equal the total amount received from the GTx, Inc. authorized representative. Damaged and/or contaminated packets must also be accounted for in the

Protocol: A Phase 2 Open Label, Multi-Center, Multinational Study Investigating The Efficacy and Safety Of GTx-024 On Advanced, Androgen Receptor-Positive Triple Negative Breast Cancer (AR+ TNBC)	Compound No.: GTx-024 Author: [name]
---	---

dispensing records. All discrepancies must be explained in writing. The study personnel responsible for study medication administration to the subject will record the date and time the initial treatment is given to the subject. In addition, the Drug Accountability electronic case report form (eCRF) will document any treatment interruptions or discontinuations.

## 6.5 Assessment of Subject Compliance with Study Investigational Product

Subjects should be instructed to return all unused study medication and containers at each clinic visit during the clinical trial period so that drug accountability can be performed. The dispensing pharmacy is required to count all returned study capsules and record this on the proper eCRF.

All study medication returned by subjects must be accounted for and verified by the study monitor. After verification of all study medication, return of used packages and unused study medication must be authorized by the study monitor before being returned to GTx, Inc., or authorized representative.

## 6.6 Concomitant Medications/Treatments

Forbidden medications and treatments during the study duration include:

- Major surgery within 28 days before the first dose of study treatment;
- Testosterone, methyltestosterone, oxandrolone (Oxandrin®), oxymetholone, danazol, fluoxymesterone (Halotestin®), testosterone-like agents (such as dehydroepiandrosterone, androstenedione, and other androgenic compounds, including herbals), Previous therapy with testosterone and testosterone-like agents is acceptable with a 28-day washout (if previous testosterone therapy was long-term depot within the past 6 months, the site should contact the Medical Monitor)
- Any prior or current use of anti-androgens including enzalutamide and bicalutamide;
- Treatment with any of the following hormone replacement therapies within 28 days before the first dose of study treatment:
  - Estrogens
  - Megesterol acetate;
- Treatment with any investigational agent within 28 days before the first dose of study treatment;
- Local palliative radiotherapy or localized radiotherapy for lytic lesions at risk of fracture within 7 days prior to the first dose of study treatment;
- Radiotherapy within 14 days prior to the first dose of study treatment.. Subjects must have recovered from radiotherapy toxicities prior to the first dose of study treatment;
- Any antineoplastic treatment (including, but not limited to chemotherapy);.

Protocol: A Phase 2 Open Label, Multi-Center, Multinational Study Investigating The Efficacy and Safety Of GTx-024 On Advanced, Androgen Receptor-Positive Triple Negative Breast Cancer (AR+ TNBC)	Compound No.: GTx-024 Author: [name]
---	---

- Caution should be exercised when administering potent CYP3A4 inducers, UDP inhibitors, and substrates of BCRP with GTx-024. Drug-drug interaction studies conducted with GTx-024 3 mg have demonstrated that concomitant use of CYP3A4 inducers may decrease the rate and extent of exposure of GTx-024 and its glucuronide metabolite. UDP inhibitors may increase GTx-024 and glucuronide exposure. Concomitant administration of GTx-024 with BCRP substrates may lead to increased exposure of the BCRP substrate.

Protocol: A Phase 2 Open Label, Multi-Center, Multinational Study Investigating The Efficacy and Safety Of GTx-024 On Advanced, Androgen Receptor-Positive Triple Negative Breast Cancer (AR+ TNBC)	Compound No.: GTx-024 Author: [name]
---	---

## 7 STUDY SCHEDULE

Subjects with CB at 16 weeks will continue on therapy as long as they are still benefitting from the treatment. Treatment may continue for up to 12 months from the date of the first dose of study treatment (as long as they continue to demonstrate CB from the treatment during these 12 months).

Subjects who continue to demonstrate a beneficial response from the study treatment at 12 months will be offered to continue in a safety extension study under a separate protocol.

All visits may be scheduled within a time window of  $\pm 7$  days.

### 7.1 Screening

For potential subjects without documented evidence of AR+ status, a Prescreening period is allowed any time prior to the Screening assessment (Visit 1), in order to determine AR status through a local laboratory. Should your institution require consent from the potential subject for prescreening tests, a separate prescreening consent should be obtained. Subjects will not be assigned a study number during the Prescreening period. Once AR status is determined to be positive, the potential subject must sign the full study consent form and may proceed to the Screening Visit (Visit 1).

Screening assessments must occur within 28 days prior to the first dose of study treatment for determination of subject's overall eligibility. Informed consent will be obtained from the subjects before performing any other study procedure or test. AEs will be collected from the signing of the informed consent form (ICF). The following tests and procedures will be performed during the screening visit (Visit 1):

- Eligibility criteria check
- Subject medical history (current and past)
- Demography (age, gender, race)
- Diagnosis and extent of cancer
- Review of prior/concomitant medications, including previous and current anticancer treatment
- Physical examination, including height, weight, and vital signs (heart rate, respiratory rate, temperature, blood pressure in a sitting position)
- ECOG performance status
- ECG
- Blood sampling for: screening for HIV, HBV, and HCV

Protocol: A Phase 2 Open Label, Multi-Center, Multinational Study Investigating The Efficacy and Safety Of GTx-024 On Advanced, Androgen Receptor-Positive Triple Negative Breast Cancer (AR+ TNBC)
	
Compound No.: GTx-024 Author: [name]

--	---

- Blood sampling for hematology, biochemistry, coagulation status, and serum pregnancy test (if applicable)
- Blood sampling for specific blood tests: PSA
- Urine analysis
- AE collection (from the moment of ICF signing)
- Radiological evaluation of the breast cancer (as applicable CT/MRI/bone scan). Imaging results will be confirmed by a central imaging facility, although a subject will be enrolled based on the local imaging and Investigator's assessment. The central imaging facility will also perform tumor volumetric assessment for the subjects undergoing CT scanning. It is recommended these procedures are done as close to the baseline visit as possible (if possible within 7 days prior to baseline)
- Review of medical history to confirm the hormonal receptor status of the tumor (HER2, ER, PR)
- AR status will be locally assessed via nuclear AR staining by IHC, only if it is not available in the medical record of the subject. This assessment will be done in a local/regional laboratory and confirmed at a central laboratory

## 7.2 Baseline

The following tests and procedures will be performed during the baseline visit (Visit 2), or results checked and confirmed:

- Eligibility criteria checked
- Review of prior/concomitant medications, including previous and current anticancer treatment
- Vital signs (heart rate, respiratory rate, temperature, blood pressure in a sitting position), if not done within the last 7 days
- ECOG performance status, if not done within the last 7 days
- Blood sampling for: hematology, biochemistry, and PSA if not done within the last 7 days; and serum lipid profile, serum hormones, and CTCs (enumeration and gene expression)
- Urine analysis, if clinically indicated
- AE collection
- Subjects will be asked to complete a QoL questionnaire
- Urine pregnancy test for premenopausal subjects (will be done at the site with a pregnancy stick test)
- First dose to subject at this visit. Subject will be given a carton box of 10 blister cards containing GTx-024
- Blood sample for pharmacokinetic assessment. The baseline blood sample should be collected before the subject is given their first dose of GTx-024. The exact time (hh:mm)

Protocol: A Phase 2 Open Label, Multi-Center, Multinational Study Investigating The Efficacy and Safety Of GTx-024 On Advanced, Androgen Receptor-Positive Triple Negative Breast Cancer (AR+ TNBC)	Compound No.: GTx-024 Author: [name]
---	---

and date of the blood sample will be recorded on the eCRF.

### 7.3 Treatment Phase

The first dose of study drug will be administered at baseline (Visit 2). GTx-024 will be administered for up to 12 months from the first dose of treatment or until disease progression (whichever is sooner), subject's withdrawal of consent, or intolerability. Subjects who benefit from the treatment at week 16 and still benefit from the treatment at week 24 may continue to receive GTx-024 for a total of 12 months from the date of the first dose of study treatment (as long as they still benefit from the treatment during these 12 months). Subjects who continue to demonstrate a beneficial response at 12 months will be offered to continue in a safety extension study under a separate protocol.

After randomization on Day 1, a safety check involving a comprehensive metabolic panel (Chem 14), including serum calcium and liver function tests, will be performed at Week 2 ( $\pm 3$  days). The Week 2 safety check should include a clinic visit. The investigator may repeat these checks at Week 3 ( $\pm 3$  days) if clinically indicated.

During the first 4 months of the treatment phase, the subjects will be asked to come for a visit every 4 weeks (Visits 3, 4, 5, and 6), and then every 8 weeks (Visit 8 and Visits 10–12 as required if still on treatment). Visits 7 and 9 at weeks 20 and 28 will only take place in subjects who have CR or PR at Visit 6 (week 16) or Visit 8 (week 24), respectively (see below).

The following tests and procedures will be performed during Visits 3, 4, 5, 6, and 8 in the treatment phase:

- Review concomitant medications
- Physical examination, including weight and vital signs (heart rate, respiratory rate, body temperature, blood pressure in a sitting position)
- ECOG performance status
- Blood sampling for: hematology, biochemistry, serum lipid profile, coagulation status, serum hormones, and PSA
- Urine analysis, only if clinically indicated
- Urine pregnancy test for premenopausal subjects (at the site)
- AE collection
- Subjects will be asked to complete a QoL questionnaire
- GTx-024 drug accountability/dispensation

Radiologic assessments for anti-tumor effect will be done every 8 weeks whilst subjects receive treatment (Visit 4, Visit 6, Visit 8, and thereafter). In addition, if a subject has CR or PR at Visit 6 (week 16) or Visit 8 (Week 24), in compliance with RECIST 1.1 guidelines, a confirmation of the CR or PR should be done 4 weeks later (i.e., Visit 7 and/or Visit 9, as

Protocol: A Phase 2 Open Label, Multi-Center, Multinational Study Investigating The Efficacy and Safety Of GTx-024 On Advanced, Androgen Receptor-Positive Triple Negative Breast Cancer (AR+ TNBC)	Compound No.: GTx-024 Author: [name]
---	---

applicable). The same imaging technique must be used throughout the study in a given subject. Bone scans will be performed at screening and then at weeks 8, 16, and 24 in only those subjects with baseline bone metastases, or if clinically indicated. The central imaging facility will also perform tumor volumetric assessment for the subjects undergoing CT scanning during Visit 6 and Visit 8. Blood sampling for CTC enumeration will be done at the same visits as the radiological assessments during the treatment phase; i.e., every 8 weeks whilst subjects receive treatment (Visits 4, 6, and 8), but not at the confirmation of the CR or PR visits (Visits 7 and 9) or at Visits 10–12.

Dispensing of GTx-024 will be done every 8 weeks: at Visit 4 (week 8), Visit 6 (week 16), Visit 8 (if subject continues treatment after week 24), and thereafter if a subject continues treatment every 8 weeks.

Blood samples for pharmacokinetic assessment will be collected at Visit 3 (week 4), Visit 5 (week 12), Visit 6 (week 16), and Visit 8 (week 24). The exact time (hh:mm) and date of each blood sample will be recorded on the eCRF. The date and approximate time of the last dose of GTx-024 prior to the blood sample should also be recorded; i.e., it should be documented whether the subject took the previous dose that morning or the evening before.

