## 8.2.2 Special Assays or Procedures

### Pharmacokinetic assessment:

Blood samples for pharmacokinetic assessment will be collected at baseline (pre-dose), Visit 3 (week 4), Visit 5 (week 12), Visit 6 (week 16), and Visit 8 (week 24). One blood sample will be collected in a 6 mL K2-ethylenediaminetetraacetic acid (EDTA) blood collection tube on each of these days. The exact time (hh:mm) and date that each blood sample is collected will be

Protocol: A Phase 2 Open Label, Multi-Center, Multinational Study Investigating The Efficacy and Safety Of GTx-024 On Advanced, Androgen Receptor-Positive Triple Negative Breast Cancer (AR+ TNBC)	Compound No.: GTx-024 Author: [name]
---	---

recorded on the eCRF. At the baseline visit, the blood sample should be collected before the subject is given their first dose of GTx-024. At visits 3 (week 4), 5 (week 12), 6 (week 16), and 8 (week 24), the date and approximate time of the last dose of GTx-024 prior to the blood sample should be recorded; i.e., it should be documented whether the subject took the previous dose that morning or the evening before. Immediately after collection, the tubes will be gently inverted several times to mix the anticoagulant with the blood sample.

Blood samples will be kept on wet ice (ice packs in a water bath is also acceptable) for up to 20 minutes until processed. The plasma fraction will be separated by placing the collection tube into a centrifuge for 10 minutes at 1,500 x g. The plasma fraction will be withdrawn by pipette and divided into two 2 mL polypropylene transfer vials (with each tube receiving approximately equal aliquots).

All sample collection and freezing tubes will be clearly labeled in a fashion which identifies the subject, the study number, the visit number, and freezing tube aliquot letter. Labels will be fixed to freezing tubes in a manner that will prevent the label from becoming detached after freezing. Samples will be stored in a freezer at  $-20^{\circ}\text{C}$  or lower. Samples will be shipped in a thermal insulated container with sufficient dry ice to assure they remain frozen.

Any remaining plasma samples after completion of the protocol outlined pharmacokinetic analysis may be used to identify and quantify the metabolites of GTx-024.

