#### 11.4.3.6 Pharmacokinetic analyses

- Descriptive statistics will be used to summarize the plasma concentrations of GTx-024 18 mg and GTx-024 glucuronide at each assessment.

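### On-treatment PK samples have no fixed relation to dosing, the last-dose time may be recorded as just morning or evening, and the planned analyses use neither time since dose nor actual dose

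*Combined protocol and SAP*

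**What the plan says.** **Sampling.** Section 8.2.2 sets PK samples at baseline and at weeks 4, 12, 16 and 24: "One blood sample will be collected in a 6 mL K2-ethylenediaminetetraacetic acid (EDTA) blood collection tube on each of these days". Only the first is tied to dosing: "At the baseline visit, the blood sample should be collected before the subject is given their first dose of GTx-024". Section 6.2 asks for a consistent daily dosing time but does not fix morning or evening.

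**Recording.** Section 7.3 is exact about the sample: "The exact time (hh:mm) and date of each blood sample will be recorded on the eCRF". For the dose it is looser: "The date and approximate time of the last dose of GTx-024 prior to the blood sample should also be recorded". An i.e. follows, explaining that "it should be documented whether the subject took the previous dose that morning or the evening before". The same two-part instruction is in Section 8.2.2 and in footnote 11 of both schedules of events (Protocol Summary and Appendix A). None of these places asks for the amount of the last dose.

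**Analysis.** Section 11.4.3.6 reads: "Descriptive statistics will be used to summarize the plasma concentrations of GTx-024 18 mg and GTx-024 glucuronide at each assessment". Section 11.4.3.4 dichotomizes concentrations at the week 16 and week 24 medians and relates them to clinical benefit by logistic regression, in the evaluable subjects and the FAS. Neither section mentions time since dose or actual dose.

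**Dose changes.** Under Section 6.3 a subject "may have a dose reduction from 18 mg to 9 mg per day or a drug interruption". Section 4 repeats this, and Section 9.4 adds a study-wide move to 9 mg if its hepatotoxicity rule is met. Section 6.4 has interruptions recorded on the Drug Accountability eCRF.

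**The concern.** With once-daily dosing, a single concentration depends on the subject's exposure and on how long ago the dose was taken. If some subjects dose in the morning before the visit and others the evening before, a high value may only mean a recent dose. A sample time in hours and minutes adds little when the dose time beside it may be as coarse as morning or evening.

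Dose amount raises a similar problem. A fall in the mean across visits could reflect more subjects on 9 mg or in an interruption, yet the summary carries an 18 mg label and no rule says how such samples are handled.

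Two things depend on these values: the descriptive PK objective, and the tertiary objective relating plasma concentration to clinical benefit at weeks 16 and 24. In the second, timing noise moves subjects across the median and blurs any association.

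**Working it through.** The plan states no PK figure, sample size or precision, so there is nothing of its own to reproduce. The question is how far sampling time alone disturbs the median split, and how much of that the data already requested could repair.

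**Inputs from the documents:** once-daily dosing (24 h interval); one sample per visit; morning and evening dosing both expected; up to 41 evaluable subjects.

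**Assumed, because the documents give no values:** one-compartment oral model at steady state; absorption rate ka = 1/h; half-life 12 to 48 h; lognormal exposure with CV 30%; half the subjects sampled 1 to 6 h after a morning dose and half 12 to 18 h after an evening dose.

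**Formula.** With ke = ln 2 / half-life, the concentration t hours after a dose is proportional to

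ka/(ka − ke) × [exp(−ke·t)/(1 − exp(−24·ke)) − exp(−ka·t)/(1 − exp(−24·ka))].

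Example, half-life 24 h: ke = 0.693/24 = 0.0289. The expression is 1.805 at 2 h and 1.297 at 16 h, a ratio of 1.39 at identical exposure.

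**Misclassification.** Draw true log exposure from a normal distribution with SD = √ln(1 + 0.30²) = 0.294, add the log of the expression at a random sampling time, and count subjects whose true and observed values fall on opposite sides of their medians. Then repeat after centring log concentrations within the morning and evening groups, which uses only the two-way answer.

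| Half-life (h) | Peak/trough | Morning/evening mean ratio | Wrong side, unadjusted | Wrong side, morning/evening flag used |
|---|---|---|---|---|
| 12 | 3.2 | 1.8 | 34% | 8% |
| 18 | 2.2 | 1.5 | 25% | 6% |
| 24 | 1.8 | 1.3 | 19% | 4% |
| 36 | 1.5 | 1.2 | 13% | 3% |
| 48 | 1.3 | 1.15 | 10% | 2% |

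If all 41 evaluable subjects gave a sample, the unadjusted range is 0.34 × 41 ≈ 14 down to 0.10 × 41 ≈ 4 subjects. With the flag it is 0.08 × 41 ≈ 3 down to 0.02 × 41 ≈ 1.

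**Sensitivity.** With an absorption half-life of 0.5 h, windows of 1 to 8 h and 11 to 20 h, half-lives of 6 to 48 h and CVs of 30% to 50%, the unadjusted figure runs from 45% down to 6%.

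**Dose.** If exposure is proportional to dose (also assumed), a fraction f of samples taken at 9 mg lowers the mean reported as 18 mg by f/2: 5% when f = 10%, 15% when f = 30%.

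**The case against.** The strongest reply is that the protocol already asks for enough. Section 8.2.2 requires that "the date and approximate time of the last dose of GTx-024 prior to the blood sample should be recorded". A site that follows those words supplies an approximate time since dose. A reader might infer that the dose is recorded only as morning or evening and that the timing is lost for good; the text does not support that. What stands is narrower: the i.e. makes the two-way answer sufficient, so the precision obtained will depend on the site.

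Second, most of the calculated error comes from ignoring the morning/evening answer, which is collected. This is correct, and it makes the point mainly one about analysis.

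Third, a reader might infer a rule that samples taken at 9 mg are pooled and reported as 18 mg. There is none. The 18 mg label also serves as the regimen's name elsewhere in the protocol. Interruptions are on the Drug Accountability eCRF, returned capsules are counted (Section 6.5), and the date of the last dose would itself reveal an interruption. These samples should be largely identifiable, so what is missing is a handling rule. The per-protocol set's requirement of at least 80% of the anticipated 18 mg dose (Section 11.4.1) does not supply one, because the exposure analysis is specified for the evaluable subjects and the FAS.

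Fourth, Section 11 calls itself an overview and leaves detail to a separate SAP whose text is not in the supplied document. That SAP could add the adjustment. It could not add a clock time that was never collected.

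**Conclusion.** The point holds in a limited form. On-treatment samples have no fixed relation to dosing, the recording instruction lets a site stop at morning or evening, and the analyses as described use neither time since dose nor actual dose.

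Under the assumed model the unadjusted median split misplaces about 34% to 10% of subjects for half-lives of 12 to 48 h. Using the morning/evening answer alone reduces this to about 8% to 2%. An accurate clock time would remove the remainder under that model. These sizes rest on assumed half-life, absorption rate, exposure CV, sampling windows and dosing mix. With a long half-life the effect is small.

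It would be wrong to infer any effect on the trial's main conclusion. The clinical benefit test in the evaluable subjects does not use concentrations. Only the descriptive PK objective and one tertiary analysis are affected, so this is a minor improvement.

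**What to change.** 1. **Analysis (Sections 11.4.3.4 and 11.4.3.6, or the SAP).** Adjust concentrations for, or group them by, time since dose and actual dose at sampling, both in the summaries and before any split for the clinical benefit model. Identify samples taken at 9 mg or during an interruption separately, and do not report them as 18 mg.
2. **Recording (Sections 7.3 and 8.2.2, and footnote 11 of both schedules of events).** Delete the i.e. explanation. Ask for the date, clock time (hh:mm, estimated if necessary) and number of capsules of the last dose before the sample.

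Interruptions can be linked from the Drug Accountability eCRF, so no new flag is needed. The change adds no visit, sample or change in patient management. It costs a little more eCRF and analysis work, and evening dose times will depend on subject recall. The recording change has to be in place before samples are taken; the analysis change can be made at any time before the analysis is run.
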